12. DEVICE ACCOUNTABILITY

12.1. Receipt of Study Device

Upon receipt of the study device supplies, an inventory must be performed and the device accountability log filled out and signed by the person accepting the shipment. It is important that the designated study staff counts and verifies that the shipment contains all the items noted in the shipment inventory. Any damaged or unusable study devices in a given shipment will be documented in the study files. The investigator must notify the study sponsor of any damaged or unusable study devices that were supplied to the investigator's site.

12.2. Use of Study Device

Use of device will be documented in a CRF module for each subject. Any unused devices must be returned to the sponsor at the end of the study or before product expiration date.

12.3. Return or Destruction of Study Device

At the completion of the study, there will be a final reconciliation of study devices shipped, devices used, and devices remaining. This reconciliation will be logged on the device accountability log. Any discrepancies noted will be investigated, resolved, and documented prior to return or destruction of unused study devices. Devices destroyed onsite will only be upon written instruction from the sponsor and will be documented in the study files. When a Masimo device deficiency is observed, every effort should be made to return the device and its packaging to the Sponsor in a timely manner.

13. STATEMENTS OF COMPLIANCE

This document is a clinical investigational plan for a human research study sponsored by Masimo Corporation. The study will be conducted in accordance with the ethical principles that have their origin in the Declaration of Helsinki.

By participating in the study, the Investigator agrees to adhere to all stipulations of this protocol, the conditions of the IRB or Research Ethics Committee approval, federal and local regulatory requirements, 21 CFR 812, ISO-14155, ICH GCP guidance.

The protocol, ICFs, recruitment materials, and all subject materials will be submitted to the IRB for review and approval. Approval of both the protocol and the consent form must be obtained before any subject is enrolled. Any amendment to the protocol will require review and approval by the IRB before the changes are implemented to the study.

14. INFORMED CONSENT PROCESS

See subsection on *Informed Consent Process* under *Study Procedures*.

15. ADVERSE EVENTS, ADVERSE DEVICE EFFECTS, AND DEVICE DEFICIENCIES

15.1. Definitions

The definitions for adverse event, adverse device effect, serious adverse event, serious health threat, serious adverse device effect, and unanticipated adverse device effect, device deficiencies are provided below (ISO 14155, 21 CFR 812.3(s)).

- **adverse event**: untoward medical occurrence, unintended disease or injury, or untoward clinical signs (including abnormal laboratory findings) in subjects, users or other persons, whether or not related to the investigational medical device and whether anticipated or unanticipated (ISO 14155)
- **adverse device effect**: adverse event related to the use of an investigational medical device
- **serious adverse event**: adverse event that led to any of the following:
 - a) death
 - b) serious deterioration in the health of the subject, users, or other persons as defined by one or more of the following:
 - 1) a life-threatening illness or injury, or
 - 2) a permanent impairment of a body structure or a body function including chronic diseases, or
 - 3) in-subject or prolonged hospitalization, or
 - 4) medical or surgical intervention to prevent life-threatening illness or injury, or permanent impairment to a body structure or a body function,
 - c) fetal distress, fetal death, a congenital abnormality, or birth defect including physical or mental impairment

Note: Planned hospitalization for a pre-existing condition, or a procedure required by the *Clinical Investigation Plan*, without serious deterioration in health, is not considered a serious adverse event.

- **serious health threat**: signal from any adverse event or device deficiency that indicates an imminent risk of death or a serious deterioration in the health of subjects, users or other persons, and that requires prompt remedial action for other subjects, users or other persons.

Note: This would include events that are of significant and unexpected nature such that they become alarming as a potential serious health hazard or possibility of multiple deaths occurring at short intervals.

- serious adverse device effect: adverse device effect that has resulted in any of the consequences characteristic of a serious adverse event
- unanticipated serious adverse device effect: serious adverse device effect which by its nature, incidence, severity or outcome has not been identified in the current risk assessment

Note: Anticipated serious adverse device effect (ASADE) is an effect which by its nature, incidence, severity or outcome has been identified in the risk assessment.

- device deficiency: inadequacy of a medical device with respect to its identity, quality, durability, reliability, usability, safety or performance

Note 1: Device deficiencies include malfunctions, use errors, and inadequacy in the information supplied by the manufacturer including labeling.

Note 2: This definition includes device deficiencies related to the investigational medical device or the comparator.

15.2. List of Anticipated Adverse Events

15.2.1. Anticipated Device-Related Adverse Events

The following would be considered as anticipated device-related adverse events: redness or itching at the site of sensor application, irritation or bruising at the site of sensor application, numbness or swelling at the site of sensor application, skin injury due to sensor placement on one finger for more than eight hours, injury due to tight sensor placement, choking due to small parts, and fire due to placement of device near flammable gases. For all other safety and performance warnings, subjects should refer to the study devices *Directions for Use* documents. Subjects should contact Study Staff as soon as possible if they experience a device-related adverse event while using the device at home.

15.2.2. List of Non-Reportable Adverse Events

Events related to expected post-surgical complications shall be recorded in the eCRF as data for clinical outcomes assessments but not reported as adverse events.

The following examples would be considered as non-reportable adverse events: all expected postoperative events such as but not limited to anemia, postoperative pain, itching outside of operative site location, bruising outside of operative site location, bleeding, swelling outside of operative site location, and drainage from the operative site.

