5.2.2. Risks Associated with Participation in the Clinical Investigation

A *Clinical Investigation Risk Assessment* has been conducted and documented for risks associated with blood pressure variation using pharmaceuticals, invasive arterial blood gas measurement and other study related procedures.

In order to further minimize risks specified below, study staff will use subjects' answers to a health questionnaire to inform study eligibility and determine if subjects can safely participate in the study. Subjects will be encouraged to let study staff know if they have any concerns. If subjects experience risks (including but not limited to the risks specified above), study staff will determine if the subject can safely continue participation in the study.  While most of the anticipated risks specified in these sections are anticipated to be temporary, all adverse events will be recorded and followed up as appropriate (see [Section 15](#)).

We will reduce the risk of inflicted knowledge by assuring the subjects that device readings are for research use only.

 Note: Though extremely unlikely, complications from the study may result in death. The study would most likely be stopped by the subject or study staff long before this would occur.

- Risks Associated with Skin Preparation

Risks associated with skin preparation include but are not limited to cuts, abrasions, rash, itching skin, flushing or redness of the skin, unusually warm skin, skin inflammation, and skin irritation. Each of these discomforts and side effects are temporary and should improve over time.

If there are any cuts or abrasions near the area of sensor application, certain types of skin preparation materials may not be used on the particular location to avoid any discomfort for the subject.

- Risks Associated with Skin Refrigerant (e.g., Pain Ease, Ethyl Chloride)

Risks associated with skin refrigerant include but are not limited to changes in skin color (e.g., flushing or redness of the skin), delayed wound healing, rash, itching, and swelling.

- Risks Associated with Adhesives

Risks associated with adhesives include but are not limited to skin irritation, redness of the skin, skin inflammation, itchiness, swelling, tingling sensation, rash, changes in skin color, and headache.

Subjects who are allergic to adhesives will be excluded from participation in this study.

- Risks Associated with Shaving

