Additional risks include but are not limited to vasovagal syncope (fainting), infiltrated IV, blood clot, lightheadedness, feeling flush/warm, feeling nauseated, throwing up, seizures, sudden drop/increase in blood pressure, sudden drop/increase in heart rate, tingling sensation of face or extremities, sweating, mouth dryness, and injury from tripping over or entanglement in lines.

- Risks Associated with Arterial Cannulation

Risks associated with arterial cannulation include discomfort, pain, bleeding, decreased blood supply, swelling, infection, bruising, hematoma, and damage to the blood vessel and surrounding nerves, tendons, or tissue.

Study Title: Validation Study of Mean Arterial Pressure (MAP) Parameter of Masimo
INVSENSOR00073

Revision: 

Additional risks include but are not limited to pain, vasovagal syncope (fainting), lightheadedness, feeling flush/warm, embolization (blood clot), feeling nauseated, throwing up, seizures, sudden drop/increase in blood pressure, sudden drop/increase in heart rate, irregular heart rate (e.g., premature atrial contraction (PAC), premature ventricular contraction (PVC), ECG abnormalities), tingling sensation of face or extremities, sweating, mouth dryness, arterial occlusion, arterial laceration, loss of feeling in the hand and/or arm, loss of the hand and/or arm due to rare complications of arterial cannulation, and injury from tripping over or entanglement in lines.

- Risks Associated with [REDACTED]

Risks associated with [REDACTED] include but are not limited to mild upset stomach, trouble sleeping, dizziness, lightheadedness, flushing, tingling, headache, nausea, nervousness, shaking, fast heartbeat, and hypertension.

Subjects will be monitored closely for onset of symptoms while inducing controlled hypertension using vasoactive medications. These typically resolve quickly when blood pressure returns to baseline once infusion has stopped. The safety drug to reverse the effects of [REDACTED] is [REDACTED] and it will be administered at the discretion of a trained clinician.

- Risks Associated with [REDACTED]

Risks associated with [REDACTED] include but are not limited to chest pain or discomfort, fast or irregular heartbeat or pulse, flushing, tingling, lightheadedness, dizziness, fainting, slow heartbeat, bluish-colored lips, blurred vision, confusion, dark urine, fever, headache, sweating, hypotension, and cyanide poisoning.

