15.3. Adverse Event Reporting

- All adverse events, both anticipated and unanticipated, must be recorded in the within the CRF and in the *Adverse Event Report Form*.
- All adverse events must be promptly reported to the sponsor.
- All unanticipated adverse device effects will be also reported to both the sponsor and the IRB.
- Both serious adverse events and unanticipated adverse device effects must be reported to the sponsor within 48 hours. All other adverse events should be reported to the sponsor within five business days.

- All serious adverse events will be also reported to the IRB per IRB reporting requirements. These reports may include, but will not be limited to: date of onset, brief description of the events, their treatment, whether they resulted in death, subject hospitalization, severe or permanent disability or were life threatening, their relationship to the study device, and resolution.

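### Section 15.2.2 exempts expected postoperative events from adverse-event reporting in a study with no surgery, and conflicts with section 15.3 if line placement is treated as the operative procedure

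*Combined protocol and SAP*

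**What the plan says.** Section 15.2.2 (List of Non-Reportable Adverse Events) sets the exemption: "Events related to expected post-surgical complications shall be recorded in the eCRF as data for clinical outcomes assessments but not reported as adverse events". Its examples are "all expected postoperative events such as but not limited to anemia, postoperative pain", then itching and bruising away from the operative site, and finally "bleeding, swelling outside of operative site location, and drainage from the operative site".

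Section 15.3 (Adverse Event Reporting) sets the general rule. It states that "All adverse events, both anticipated and unanticipated, must be recorded in the within the CRF" and also in the Adverse Event Report Form, and that "All adverse events must be promptly reported to the sponsor". Serious adverse events and unanticipated adverse device effects are due to the sponsor within 48 hours, and all other adverse events within five business days. No exception is stated.

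Section 15.1 defines an adverse event "whether or not related to the investigational medical device and whether anticipated or unanticipated".

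Section 5.2.2 gives the expected harms of the invasive steps. For the arterial line: "Risks associated with arterial cannulation include discomfort, pain, bleeding, decreased blood supply, swelling, infection, bruising, hematoma", and the list continues. The venous-cannulation list also names pain, bruising, bleeding and swelling. The same section says that "all adverse events will be recorded and followed up as appropriate".

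**The concern.** The exemption has no matching procedure. Section 4 describes healthy volunteers, and sections 7.6.2.2 and 7.6.3 describe a venous line, a radial arterial line, infusions and cuff measurements. The exempted events are to be kept for clinical outcomes assessments, but the only endpoint in the synopsis is the accuracy and precision of MAP, and section 8 plans no such assessment.

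With no operation to attach to, the nearest thing a site could call an operative site is a line site. Some terms in 15.2.2 are also listed risks of cannulation. Two staff members could therefore handle the same bleed differently: one files an adverse-event form, the other makes only an eCRF entry.

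What is at stake is complete and timely adverse-event reporting in volunteers who, under section 5.1, receive no direct benefit.

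**Working it through.** No figure is stated and no arithmetic applies. The check sets the sections side by side and follows typical events through them.

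**Step 1: Are the events in 15.2.2 adverse events?** Yes. The section's own heading calls them that, and under 15.1 being anticipated does not take an event out of the definition. The rule in 15.3 therefore reaches them.

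**Step 2: Does either section give way to the other?** No. Section 15.2.2 does not mention 15.3, and 15.3 carves nothing out.

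**Step 3: Which exempted terms are also cannulation risks in 5.2.2?** Pain, bleeding, bruising and swelling are in both the arterial and the venous list. Anemia, itching and drainage are in neither. In 15.2.2, bruising and swelling are limited to places away from the operative site. Bleeding has no site limit. Pain is limited only by the word postoperative.

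**Step 4: Follow typical events under two readings of 15.2.2.** The literal reading is that there is no surgery, so nothing qualifies. The broad reading treats the line site as the operative site.

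| Event | Required by 15.3 | 15.2.2, literal | 15.2.2, broad |
|---|---|---|---|
| Non-serious bleeding after arterial-line removal | Form, and sponsor within five business days | Reported | Exempt |
| Pain from line placement | Same | Reported | Exempt |
| Bruising or swelling away from the line site | Same | Reported | Exempt |
| Bruising or swelling at the line site | Same | Reported | Not covered by the listed terms; reported |
| Infection at the line site | Same, if non-serious | Reported | Not a listed term; reported |
| Serious bleeding from a line site | Form, sponsor within 48 hours, and IRB per its requirements | Reported | Exempt, since no exception for seriousness is stated |

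The list in 15.2.2 is open-ended, so the two rows marked as not covered depend on staff not extending it.

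**Step 5: What would be lost on the broad reading?** The event stays in the eCRF, because 15.2.2 requires that. Section 9.3 has CRFs provided to the sponsor and checked by the study monitor. What is lost is the adverse-event label, the Adverse Event Report Form and the 48-hour or five-business-day deadline.

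**Step 6: How many events?** About 20 subjects are planned, each with both lines. The documents give no incidence for any cannulation harm. The range therefore runs from zero (literal reading) to all line-related bleeding, procedure pain, and bruising or swelling away from the site (broad reading).

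**The case against.** The strongest reply is that 15.2.2 by its own words covers only postoperative events. The protocol speaks of line placement and cannulation and never calls a line site an operative site. With no surgery, the section is inert. It also looks like carried-over template text: 15.2.1 similarly refers to home use and to a finger sensor worn for more than eight hours, neither of which fits a laboratory cuff study. That origin is an inference, but a reasonable one. This reply stands as far as it goes, and it is why the effect is conditional. It does not justify keeping the section, because an inert rule has no use.

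A reader might also infer more than the documents support:

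- **That cannulation harms would vanish from the data.** They would not; they remain in the eCRF, which reaches the sponsor.
- **That all bruising and swelling is exempt.** Only bruising and swelling away from the operative site is listed.
- **That anemia is among the cannulation harms at risk.** It is in neither cannulation list.
- **That IRB reports of common line-site events would be lost.** Under 15.3 only serious adverse events and unanticipated adverse device effects go to the IRB, so non-serious bruising or pain would not go there anyway. The IRB path matters only for a serious event labelled postoperative.
- **That 5.2.2 is contradicted too.** It promises recording and follow-up, not reporting. Section 15.2.2 also requires recording and does not remove follow-up. The reporting conflict is with 15.3.
- **That the share of risk terms common to the two lists measures the problem.** It does not. Two of the shared terms carry a site limit, the arterial risk list is longer than the part quoted here, and a count of words says nothing about events.

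**Conclusion.** The point holds in a limited form. Section 15.2.2 is either empty (literal reading) or in conflict with 15.3 (broad reading), and nothing in the protocol settles which. On the broad reading, bleeding, procedure pain, and bruising or swelling away from the line site could be left off the Adverse Event Report Form and outside the sponsor deadlines, with no stated exception for serious events.

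The size cannot be given and may be zero. Any effect rests on one assumption that the documents neither state nor exclude: that site staff treat venous or arterial line placement as the operative procedure.

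The MAP accuracy result is not affected. Section 8 plans no adverse-event analysis, and no acceptance criterion depends on these events. This is a safety-reporting rule to reconcile, worth doing because the conflict is plain and the correction is nearly free.

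**What to change.** Delete section 15.2.2. Alternatively, replace it with a statement along these lines: *No adverse event is exempt from reporting in this study. Events related to the venous line, the arterial line, the infusions or the cuff are recorded and reported under section 15.3, whether or not they were expected.*

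The cost is one short change in a protocol amendment, with the IRB approval that section 10 requires for any amendment. There may be a few more adverse-event forms for minor line-related events, but 15.3 already requires those. Sample size, data collection and the accuracy analysis are unchanged.

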15.3. Adverse Event Reporting

- All adverse events, both anticipated and unanticipated, must be recorded in the within the CRF and in the *Adverse Event Report Form*.
- All adverse events must be promptly reported to the sponsor.
- All unanticipated adverse device effects will be also reported to both the sponsor and the IRB.
- Both serious adverse events and unanticipated adverse device effects must be reported to the sponsor within 48 hours. All other adverse events should be reported to the sponsor within five business days.

- All serious adverse events will be also reported to the IRB per IRB reporting requirements. These reports may include, but will not be limited to: date of onset, brief description of the events, their treatment, whether they resulted in death, subject hospitalization, severe or permanent disability or were life threatening, their relationship to the study device, and resolution.

15.4. Device Deficiencies Reporting

All Masimo device related deficiencies should be reported to the sponsor and must be recorded in the CRF in a timely manner. When a Masimo device deficiency is observed, every effort should be made to return the device and its packaging to the sponsor in a timely manner.

16. VULNERABLE POPULATION

16.1. Definition

Vulnerable population are research subjects, such as children, prisoners, pregnant women, handicapped, or mentally disable persons, or economically or educationally disadvantaged persons, who are likely to be vulnerable to coercion and undue influence. This study is not targeting these populations.

The federal regulations that govern the protection of human subjects require additional protection for the vulnerable population.

16.2. Protection of Vulnerable Subjects

- Reasonable compensation (i.e., travel expenses) may be provided for economically disadvantaged subjects to eliminate the possibility of undue influence due to financial incentive.
- Educationally disadvantaged subjects will be provided ample time to ask questions and comprehend information.
- Medical care will be provided to these subjects after the clinical investigation has been completed if they are injured as a direct result of participating in this research study. The cost of treatment for any research related injury will be covered by Masimo.

16.3. Responsible Parties

- The IRB will review research with vulnerable populations and evaluate consent, level of risk, coercion, and the reason for choosing this particular subject population. The IRB will be responsible for determining what practices will include continuing review for compliance while monitoring these studies.
- The Investigator holds the ultimate responsibility for protecting the rights, safety, and welfare of research subjects by ensuring that all regulations and proper documentation of consent are handled in a compliant and timely manner.

